1.2.2.3 Summary of Clinical Data in Chronic GvHD

The Th2/Th17-cells which contribute to the pathogenesis of chronic GvHD rely upon ITK to drive intracellular activation and immune reactivity towards healthy tissues. By blocking the threshold activation of ITK, ibrutinib can impede the activation of these pathogenic T-cells while still permitting immune activity against pathogenic affronts. BTK, on the other hand, is important for B-cell activation and differentiation. Inhibition of BTK has been shown to be important in ameliorating autoimmune diseases with B-cell dysfunction such as rheumatoid arthritis and lupus. Genetic studies have confirmed that ITK and BTK are independently critical for chronic GvHD and ibrutinib has demonstrated its effectiveness in both T-cell driven and alloantibody driven chronic GvHD models. In animal models of chronic GvHD, mice that were ITK or BTK deficient did not develop chronic GvHD, indicating that both BTK and ITK are important to chronic GvHD development. Since ibrutinib inhibits both BTK and ITK, ibrutinib has the potential to have an impact on both B and T cells that are critical in the pathogenesis of GvHD and may have the potential to provide a clinically meaningful benefit for patients with chronic GvHD. Preclinical results demonstrate a substantial therapeutic benefit of ibrutinib treatment to reduce the prolonged effects of chronic GvHD.

Chronic GvHD is a leading cause of non-relapse related mortality in the transplant setting and there are no approved therapies for chronic GvHD. Ibrutinib offers a novel mechanism of action as a potent inhibitor of BTK that also inhibits ITK. Ibrutinib has the potential to have an impact on both B and T cells that are critical in the pathogenesis of chronic GvHD.

In humans, phase 1/2-study of ibrutinib in 42 patients with steroid-refractory chronic GvHD showed that 420 mg/day of ibrutinib was well tolerated with a robust clinical response. Analysis of soluble plasma factors associated with inflammation, fibrosis, and chronic GvHD from treated patients showed a significant decrease over time. Overall response rate was 67%, with 71% and 48% responders showing a sustained response of ≥ 20 and ≥ 32 weeks, respectively. During the study 75% responders reduced steroids to < 0.15 mg/kg/d and 5 responders were able to discontinue steroids. Most common adverse events (AEs) were fatigue (57%), diarrhea (36%), muscle spasms (29%), nausea (26%), and bruising (24%). Grade ≥ 3 AEs were pneumonia (n=6), fatigue (n=5), and diarrhea (n=4). Serious AEs (SAEs) occurred in 52% subjects and grade ≥ 3 SAEs in 40%, included pneumonia (n=5), septic shock (n=2), and pyrexia (n=2). Two fatal events (multilobular pneumonia and pulmonary aspergillosis) were reported. Results from this trial led the FDA granting ibrutinib a breakthrough designation and in August 2017 regulatory approval for chronic GvHD after failure of one or more lines of systemic therapy. This first ever indication for the systemic treatment of chronic GvHD was given based on the results using the NIH criteria response measures. Taken together, these proof-of-principle findings support exploring ibrutinib as a treatment for newly diagnosed chronic GvHD. The phase III, randomized, multicenter, placebo control study of ibrutinib in conjunction with high-dose steroids as a front-line therapy for newly diagnosed chronic GvHD is currently in progress (NCT02959944).

TEAEs in $> 20\%$, $> 10\%$ and $> 2\%$ of Subjects who Received Ibrutinib for chronic GvHD:

Most Commonly reported TEAEs >20%	Most Commonly reported TEAEs >10%	Most Commonly reported Serious TEAEs > 2%
Fatigue Diarrhea	Fatigue Diarrhea	Fatigue Diarrhea Pyrexia Pneumonia Hypokalemia Cellulitis Stomatitis Hypertension Thrombocytopenia Dyspnea Anemia Hyperglycemia

1.2.2.4 Potential Risks and Guidance for Investigators

Based on currently available data, ibrutinib has an acceptable safety profile as monotherapy among the B-cell malignancies studied and when combined with chemo-immunotherapy. This is supported extensively by data from the randomized, comparator-controlled studies.

1.2.2.4.1 Bleeding-related events

There have been reports of hemorrhagic events in subjects treated with ibrutinib, both with and without thrombocytopenia. These include minor hemorrhagic events such as contusion, epistaxis, and petechiae; and major hemorrhagic events, some fatal, including gastrointestinal bleeding, intracranial hemorrhage, and hematuria. In an in-vitro platelet function study, inhibitory effects of ibrutinib on collagen induced platelet aggregation were observed. Initially, subjects were excluded from participation in specific ibrutinib Phase 2 and 3 studies if they required warfarin or other vitamin K antagonists. Warfarin or other vitamin K antagonists should not be administered concomitantly with ibrutinib unless specified in the protocol. Supplements such as fish oil and vitamin E preparations should be avoided. Use of ibrutinib in subjects requiring other anticoagulants or medications that inhibit platelet function may increase the risk of bleeding. Subjects with congenital bleeding diathesis have not been studied. Ibrutinib should be held at least 3 to 7 days pre- and post-surgery, depending upon the type of surgery and the risk of bleeding.

1.2.2.4.2 Infections

Infections (including sepsis, bacterial, viral, or fungal infections) were observed in subjects treated with ibrutinib therapy. Some of these infections have been associated with hospitalization and death. Consider prophylaxis according to standard of care in subjects who are at increased risk for opportunistic infections. Although causality has not been established, cases of progressive multifocal leukoencephalopathy (PML) and hepatitis B reactivation have occurred in subjects treated with ibrutinib. Cases of hepatitis E, which may be chronic, have occurred in patients treated with ibrutinib. Subjects should be monitored for symptoms (fever, chills,

weakness, confusion, vomiting, jaundice, and abnormal liver function tests) and appropriate therapy should be instituted as indicated.

1.2.2.4.3 Cytopenias

Treatment-emergent Grade 3 or 4 cytopenias (neutropenia, thrombocytopenia, and anemia) were reported in subjects treated with ibrutinib. Subjects should be monitored for fever, weakness, or easy bruising and/or bleeding. Monitor complete blood counts monthly.

1.2.2.4.4 Interstitial Lung Disease

Cases of interstitial lung disease (ILD) have been reported in subjects treated with ibrutinib. Monitor subjects for pulmonary symptoms indicative of ILD. If symptoms develop, interrupt ibrutinib and manage ILD appropriately. If symptoms persist, consider the risks and benefits of ibrutinib treatment and follow the dose modification guidelines as needed.

1.2.2.4.5 Cardiac Arrhythmias and cardiac failure

Atrial fibrillation, and atrial flutter, and cases of ventricular tachyarrhythmia and cardiac failure including some fatal events, have been reported in subjects treated with ibrutinib, particularly in subjects with cardiac risk factors, hypertension, acute infections, and a previous history of cardiac arrhythmia. At baseline and then periodically, monitor subjects clinically for cardiac arrhythmia and cardiac failure. Subjects who develop arrhythmic symptoms (e.g., palpitations, lightheadedness, syncope, chest discomfort or new onset of dyspnea) should be evaluated clinically, and if indicated, have an ECG performed. For cardiac arrhythmias or cardiac failure consider the risks and benefits of ibrutinib treatment, and follow the dose modification guidelines.

1.2.2.4.6 Tumor Lysis Syndrome

Tumor lysis syndrome has been reported with ibrutinib therapy. Subjects at risk of tumor lysis syndrome are those with high tumor burden prior to treatment. Monitor subjects closely and take appropriate precautions.

1.2.2.4.7 Non-melanoma skin cancer and Other Cancers

Non-melanoma skin cancer (basal cell carcinoma and squamous cell carcinoma of the skin) have been reported with more frequency and maybe related to the use of ibrutinib. Other cancers have been observed in patients who have been treated with ibrutinib. These include solid tumors, skin cancer, and cancers of the blood. Monitor subjects for the appearance of other cancers.

1.2.2.4.8 Diarrhea

Diarrhea is the most frequently reported non-hematologic AE with ibrutinib monotherapy and combination therapy. Other frequently reported gastrointestinal events include nausea, vomiting, and constipation. These events are rarely severe and are generally managed with supportive therapies including antidiarrheals and antiemetics. Subjects should be monitored carefully for gastrointestinal AEs and cautioned to maintain fluid intake to avoid dehydration. Medical evaluation should be made to rule out other etiologies such as *Clostridium difficile* or other infectious agents. Should symptoms be severe or prolonged, ibrutinib treatment should be modified according to protocol guidelines.

1.2.2.4.9 Rash

Rash has been commonly reported in subjects treated with either single-agent ibrutinib or in combination with chemotherapy. Most rashes were mild to moderate in severity. Isolated cases of severe cutaneous adverse reactions (SCARs) including Stevens-Johnson syndrome (SJS) have been reported in subjects treated with ibrutinib. Subjects should be closely monitored for signs and symptoms suggestive of SCAR including SJS. Subjects receiving ibrutinib should be observed closely for rashes and treated symptomatically, including interruption of the suspected agent as appropriate. In addition, hypersensitivity-related events including erythema, urticaria, and angioedema have been reported.

1.2.2.4.10 Hypertension

Hypertension has been commonly reported in subjects treated with ibrutinib. Monitor subjects for new onset of hypertension or hypertension that is not adequately controlled after starting ibrutinib. Adjust existing anti-hypertensive medications and/or initiate anti-hypertensive treatment as appropriate.

1.2.2.4.12 Stroke

Cases of stroke, with and without changes in heartbeat rhythm and/or hypertension have been reported with the use of ibrutinib. Some of these cases have led to death. Seek immediate medical attention if you notice or someone notices in you: sudden numbness or weakness in the limbs (especially on one side of the body), sudden confusion, trouble speaking or understanding

speech, sight loss, difficulty walking, loss of balance or lack of coordination, sudden severe headache with no known cause. These may be signs and symptoms of stroke.

1.2.3 Study Rationale

For more than three decades the most widely used first-line systemic therapy of chronic GvHD has been prednisone alone or in conjunction with calcineurin inhibitors (cyclosporine([52](#)) or tacrolimus [TAC]); however, this approach has a durable response rate of less than 50%.

Currently there is no FDA-approved therapy for newly diagnosed chronic GvHD and development of well-designed prospective and innovative therapeutic studies is an urgent unmet clinical need.

In this study we propose the use of ibrutinib as the front-line therapy for newly diagnosed chronic GvHD, instead of high-dose steroids. Our central hypothesis is that ibrutinib will be effective and well tolerated as a single agent, front-line systemic therapy for newly diagnosed chronic GvHD.

2 ELIGIBILITY ASSESSMENT AND ENROLLMENT

2.1 ELIGIBILITY CRITERIA

2.1.1 Inclusion Criteria

- 2.1.1.1 Newly diagnosed moderate or severe chronic Graft versus Host Disease (GvHD) (according to the 2014 NIH Consensus Criteria, requiring systemic immunosuppression)
- 2.1.1.2 History of prior allogeneic Hematopoietic Stem Cell Transplant (HSCT) (any donors, conditioning regimens and graft sources are allowed).
- 2.1.1.3 Subjects may have ongoing acute GvHD features (e.g., erythematous rash, elevated liver enzymes, diarrhea) which are in the opinion of the investigator responding to therapy.
- 2.1.1.4 Stable doses of other immunosuppressive medications (e.g., calcineurin inhibitors, mycophenolate mofetil, rapamune, etc.) with no dose increase in the 2 weeks prior to study treatment initiation. Doses may be adjusted for trough levels.
- 2.1.1.5 Age \geq 18 years old
- 2.1.1.6 Karnofsky performance status \geq 60% ([Appendix B](#))
- 2.1.1.7 Laboratory parameters as defined below:
 - Serum creatinine \leq 2.0 x ULN
 - AST and ALT \leq 3 x ULN (\leq 5 x ULN if unequivocal liver GvHD)
 - Total bilirubin \leq 3 x ULN
 - Absolute neutrophil count \geq 1.0 x 10^9 /L (no growth factor support allowed)
 - Platelets $>$ 50 x 10^9 /L (no transfusions allowed \leq 7 days prior to enrollment)
- 2.1.1.8 Ability to understand and willingness to sign a written informed consent form
- 2.1.1.9 The effects of ibrutinib on the developing fetus are unknown. For this reason and because tyrosine kinase inhibitors may be teratogenic, female subjects of childbearing

potential and men must agree to use highly effective methods of birth control (hormonal or barrier method of birth control; abstinence) prior to study entry, during the period of therapy, and for 30 days after the last dose of study drug.

2.1.2 Exclusion Criteria

2.1.2.1 Relapsed or progressive malignant disease (other than minimal residual disease

2.1.2.2 History of other malignant diseases, including post-transplant lymphoproliferative disease, with the following exceptions:

- Malignancy treated with curative intent and with no evidence of active disease present for more than 3 years prior to study treatment initiation and felt to be at low risk for recurrence
- Adequately treated non-melanomatous skin cancer or lentigo malignant melanoma without current evidence of disease
- Adequately treated cervical carcinoma in situ without current evidence of disease

2.1.2.3 Received previous systemic treatment for chronic GvHD other than ≤ 0.5 mg/kg/day of prednisone equivalent for more than 7 days. Subject may be on steroids that were used to treat acute GvHD and then developed chronic GvHD before completing a taper. At the time of enrollment, the dose should be ≤ 0.5 mg/kg/day of prednisone equivalent with no dose increase in the preceding 2 weeks before study treatment initiation

2.1.2.4 Prior or current treatment with:

- Ibrutinib since the time of transplant (participants may have received ibrutinib prior to transplant for indications other than chronic GvHD)
- Extracorporeal photopheresis (ECP) for acute GvHD ≤ 2 weeks prior to study treatment initiation; including any treatment with ECP for chronic GvHD.
- Rituximab or other anti-B cell specific antibodies ≤ 4 weeks prior to study treatment initiation.
- Any systemic investigational agents ≤ 4 weeks prior to study treatment initiation

2.1.2.5 Impaired cardiac function including any one of the following:

- Myocardial infarction, unstable angina or acute coronary syndrome ≤ 6 months prior to study treatment initiation
- Class 3 or 4 congestive heart failure, uncontrolled arrhythmia or uncontrolled hypertension at any time

- 2.1.2.6 Uncontrolled infections (including prior aspergillosis) not responsive to antibiotics, antiviral medicines, or antifungal medicines
- 2.1.2.7 Known bleeding disorder or subjects who received a strong cytochrome P450 (CYP) 3A inhibitor \leq 7 days prior to the first dose of ibrutinib or requirement for continuous treatment with a strong CYP3A inhibitor ([Appendix C](#))
- 2.1.2.8 Active hepatitis C virus (HCV) or hepatitis B virus (HBV). Subjects who are positive for hepatitis B core antibody or hepatitis B surface antigen or hepatitis C antibody must have a negative polymerase chain reaction (PCR) result to be enrolled.
- 2.1.2.9 Known hypersensitivity to ibrutinib
- 2.1.2.10 Pregnant women are excluded from this study because ibrutinib has potential for teratogenic and abortifacient effects. Because there is an unknown but potential risk for adverse events in nursing infants secondary to treatment of the mother with ibrutinib, breastfeeding should be discontinued if the mother is treated with ibrutinib. Women who are planning to become pregnant and men who plan to father a child while enrolled in this study or \leq 30 days after the last dose of study drug are excluded.
- 2.1.2.11 Any other reason at the discretion of the investigators and documented in the medical record that may raise concerns about the subject safety or ability to participate on this study
- 2.1.2.12 Currently active, severe hepatic impairment Child-Pugh class C according to the Child Pugh classification ([Appendix J](#))

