3.2.1 Dose Adjustments for participants on CYP3A4 inhibitors

Participants who are treated with certain medications that are mild and moderate CYP3A4 inhibitors will start ibrutinib at a lower dose.

A list of common CYP3A inhibitors and inducers is provided in [Appendix C](#). For further information, please refer to the current version of the ibrutinib IB and examples of inhibitors, inducers, and substrates can be found at <http://medicine.iupui.edu/clinpharm/ddis/main-table/>.

Drug	Ibrutinib dose modification
• Mild CYP3A inhibitors	420 mg once daily. No dose adjustment required
• Moderate CYP3A inhibitors	420 mg once daily. No dose adjustment required
• Voriconazole at any dose or • Posaconazole at doses less than or equal to suspension 200 mg BID	280 mg once daily
• Posaconazole suspension 200 mg TID or 400 mg BID • Posaconazole IV injection 300 mg once daily • Posaconazole delayed-release capsules 300 mg once daily	140 mg once daily
• Other strong CYP3A inhibitors	Avoid concomitant use. If these inhibitors will be used short-term (such as anti-infectives for seven days or less), interrupt IMBRUVICA

If these medications are later discontinued, ibrutinib dose may be increased to 420 mg.

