14.1.7 Incompatibilities

The use of strong CYP3A inhibitors/inducers, and grapefruit and Seville oranges should be avoided for the duration of the study. Please see table in section [Error! Reference source not found.](#) for further details on dosing with CYP3A inhibitors.

When anti-fungal agents, that have CYP3A properties are discontinued, the ibrutinib dose should be increased to 420 mg.

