16.3 APPENDIX C: INHIBITORS AND INDUCERS OF CYP3A

Inhibitors of CYP3A are defined as follows. A comprehensive list of inhibitors can be found at the following website: <http://medicine.iupui.edu/clinpharm/ddis/table.aspx>. The general categorization into strong, moderate, and weak inhibitors according to the website is displayed below. Refer to Section 4.4.1 and 14.1.7 on instructions for concomitant use of CYP3A inhibitors and inducers with study medications.

Inhibitors of CYP3A	Inducers of CYP3A

Strong inhibitors:
 
INDINAVIR NELFINAVIR RITONAVIR CLARITHROMYCIN ITRACONAZOLE KETOCONAZOLE NEFAZODONE SAQUINAVIR TELITHROMYCIN
 
Moderate inhibitors:
 
aprepitant erythromycin diltiazem flucanazole grapefruit juice Seville orange juice verapamil
	
Weak inhibitors:
 
cimetidine
 
All other inhibitors:
 
amiodarone NOT azithromycin chloramphenicol boceprevir ciprofloxacin delavirdine diethyl-dithiocarbamate fluvoxamine gestodene imatinib mibepradil mifepristone norfloxacin norfluoxetine star fruit telaprevir troleandomycin voriconazole
 
Carbamazepine Efavirenz Nevirapine Barbiturates Glucocorticoids Modafinil Oxcarbazepine Phenobarbital Phenytoin Pioglitazone Rifabutin Rifampin St. John's Wort Troglitazone

Source: <http://medicine.iupui.edu/clinpharm/ddis/table.aspx>

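### Voriconazole and posaconazole are classed inconsistently as CYP3A inhibitors, so whether a patient taking either at screening may enrol depends on which section is read

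*Combined protocol and SAP*

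**What the plan says.** Four places in the combined protocol and SAP bear on this.

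- **2.1.2.7 (exclusion).** It excludes "subjects who received a strong cytochrome P450 (CYP) 3A inhibitor" in the 7 days before the first ibrutinib dose, and also anyone with a "requirement for continuous treatment with a strong CYP3A inhibitor". It cites Appendix C.
- **3.2.1 (dose adjustments).** The opening sentence reads: "Participants who are treated with certain medications that are mild and moderate CYP3A4 inhibitors will start ibrutinib at a lower dose". The table then keeps mild and moderate inhibitors at 420 mg. It gives 280 mg for the row that begins "Voriconazole at any dose or" (which also covers lower-dose posaconazole suspension) and 140 mg for the row that begins "Posaconazole suspension 200 mg TID or 400 mg BID" (which also covers the listed intravenous and delayed-release posaconazole regimens). The last row is "Other strong CYP3A inhibitors": avoid, or interrupt ibrutinib if the other drug is needed only briefly.
- **14.1.7 (incompatibilities).** "The use of strong CYP3A inhibitors/inducers, and grapefruit and Seville oranges should be avoided for the duration of the study". The same section then refers the reader to a dosing table for CYP3A inhibitors and says what to do when an antifungal with CYP3A activity is stopped.
- **Appendix C (inhibitors and inducers).** Nine drugs are listed as strong, and neither azole is one of them. Voriconazole comes at the end of the residual group of inhibitors ("star fruit telaprevir troleandomycin voriconazole"). Posaconazole does not appear.

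**The concern.** An eligibility rule and a dosing table that both depend on the word strong need the same list of strong drugs behind them. Here the list that the exclusion cites and the list that the dosing table implies differ for two named antifungals.

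The situation is foreseeable. Section 2.1.2.3 admits patients on up to 0.5 mg/kg/day of prednisone equivalent, and 4.1.2 allows a pulse of 0.5 to 2 mg/kg/day in the first 4 weeks. Section 4.3 recommends mould-active prophylaxis above 0.20 mg/kg/day, naming isavuconazole but permitting a substitute. Some candidates may therefore arrive on an azole or be started on one.

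What is at stake is who enters a small multi-centre trial, and whether screening staff can apply the exclusion uniformly. It is also a safety matter, because the exclusion and the table both exist to manage interacting drugs. The pharmacokinetic samples, which are meant to be related to response and toxicity, come from whichever patients are let in.

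**Working it through.** No arithmetic tests this point; it is a comparison of texts. How each place treats the two azoles:

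| Place | Voriconazole | Posaconazole | How stated |
|---|---|---|---|
| 2.1.2.7 | not named | not named | defers to Appendix C |
| Appendix C | residual group, not strong | not listed | explicit for voriconazole; silent for posaconazole |
| 3.2.1 table | strong | strong | by implication, from the word Other in the last row |
| 3.2.1 opening sentence | not named | not named | only mild and moderate classes are said to start lower |
| 14.1.7 | not named | not named | avoid strong inhibitors, yet expects antifungals with CYP3A activity |

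**Reading A: the classification implied by the 3.2.1 table.** Both azoles are strong.
1. Under 2.1.2.7, a patient who took either within 7 days of the first dose, or who needs it continuously, is excluded.
2. The azole rows can then serve only treatment begun after entry.
3. Even that use fits poorly with the first sentence of 14.1.7, although the rest of 14.1.7 foresees antifungal co-medication.

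**Reading B: the classification in Appendix C.** Neither azole is on the strong list.
1. Exclusion 2.1.2.7 does not reach them.
2. The patient may enrol and the 3.2.1 rows supply a dose, so eligibility and dosing agree.
3. The last row of the 3.2.1 table then has nothing for its word Other to refer back to.

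The same patient is thus ineligible under A and eligible under B, and no sentence says which governs.

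**When the rows apply.** The opening sentence of 3.2.1 concerns the dose at which ibrutinib is started, and the sentence after the table covers the interacting drug being stopped later. Both describe a patient already on the interacting drug at the first dose, which is when 2.1.2.7 is applied. Nothing confines the rows to drugs begun after entry.

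**The opening sentence against its table.** The sentence lowers the starting dose for certain mild and moderate inhibitors. The table leaves 420 mg in place for both classes, with no exception. The only rows with a reduced dose are the azole rows. Taken literally, the sentence would place the azoles with the mild and moderate drugs, against the implication of the last row. Section 3.2.1 is therefore unclear on its own terms, before Appendix C is considered.

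**Scale.** Section 10.2 plans 25 evaluable subjects, so one disputed admission is 1/25 = 4% of that set. The number of such patients cannot be derived.

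**The case against.** The strongest reply is that the exclusion names its own list. Appendix C introduces its table as the definition of CYP3A inhibitors, neither azole is among its strong drugs, and on that footing 2.1.2.7 and 3.2.1 agree. No row in 3.2.1 calls either azole strong; the inference rests on one word. Section 14.1.7 points on to a dosing table and expects interacting antifungals, and an entry exclusion can coexist with a table for drugs started later.

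Much of this stands. A reader might infer a flat contradiction between eligibility and dosing. The documents do not support that, because one available reading reconciles the two and the other reading depends on an implication. What the reply does not do is settle the matter. Appendix C sends the reader to a website for the fuller list, and 4.4.1 says that site keeps changing, so the absence of posaconazole decides nothing. The wording of 3.2.1 about starting dose also prevents the rows from being confined to later use.

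Two other inferences should be resisted:

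- **A 3-fold dose ambiguity (420/140 = 3).** The 420 mg rows are for mild and moderate inhibitors and the 140 mg row is for particular posaconazole regimens, so the ratio compares different co-medications. Each listed azole regimen has one tabulated dose. It follows that the documents do not show two sites giving different ibrutinib doses for the same listed regimen; the open question is enrol or exclude.
- **Routine use of these azoles under 4.3.** That section names isavuconazole and only allows an alternative. It names neither disputed drug.

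**Conclusion.** The point holds as an internal inconsistency of classification. Section 3.2.1 and Appendix C treat voriconazole and posaconazole differently, and this leaves the eligibility of a patient on either drug at screening undetermined. If the azoles count as strong, the 3.2.1 rows also sit uneasily with 14.1.7. Separately, the opening sentence of 3.2.1 and its table disagree about mild and moderate inhibitors, and this does not depend on how the azoles are classed.

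The conclusion rests on two readings: that Other in the last row of the table refers back to the azole rows, and that voriconazole belongs to the residual group in Appendix C, whose columns run together in the available text. In either case it is not among the nine drugs printed as strong.

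The consequence is an enrol-or-exclude ambiguity of unknown frequency, worth 4% of the evaluable set per patient affected. The two-stage design's error rates and sample size do not change. The point should be corrected because it touches safety and the make-up of a small trial, and the correction is cheap.

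**What to change.** The sponsor should reconcile 2.1.2.7, 3.2.1 (opening sentence and table), 14.1.7 and Appendix C so that they give:

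1. one classification of voriconazole and of posaconazole, used in all four places;
2. one statement of whether a patient on either drug at screening may enrol;
3. one statement of whether the azole rows in 3.2.1 apply at the start of ibrutinib, to drugs begun after entry, or to both;
4. an opening sentence in 3.2.1 that agrees with the table on mild and moderate inhibitors.

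Which classification, dose or rule is right is for the sponsor to decide; none is proposed here.

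The cost is amendment wording in four places. No change to the design, sample size or analysis is needed. If patients on either azole have already been screened, the report should say which reading was applied and how many were affected. Section 6.1 already requires all medications taken during the study to be recorded, and 2.2.2.1 covers prior and concomitant medications at screening, so this should need no new data collection.
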